### 3.0 STUDY POPULATION

Patients  $\geq$  17 years of age who are scheduled to undergo uncomplicated unilateral cataract surgery and who meet all study entry criteria. Approximately 240 subjects will be enrolled in the United States.

#### 3.1 Inclusion Criteria

The following are inclusion criteria for prospective study subjects to be confirmed at Visit 1 (Day -14 – Day -2) prior to randomization. The sponsor will not grant any protocol eligibility waivers.

- a. Are  $\geq$  17 years of age at Visit 1 (Day -14 Day -2) prior to randomization, of either sex and any race, and scheduled for uncomplicated unilateral cataract surgery (phacoemulsification or extracapsular extraction) with posterior chamber intraocular lens implantation
- b. Signature of the subject or parent(s) or legally authorized representative on the Informed Consent Form (ICF), and when appropriate the minor's assent in accordance with local regulations
- c. Are willing and able to follow all instructions and attend all study visits
- d. Are willing to avoid disallowed medication for the duration of the study
- e. If female is of childbearing potential, agree to and submit a urine sample for pregnancy testing (prior to enrollment and at the end of the study), and use effective contraception for the duration of the study
  - Male subjects whose female partners are not post-menopausal must agree to one of the following: 1) completely abstain from sexual intercourse, 2) use a barrier method (condoms) with spermicide during sexual intercourse for the duration of the study, 3) provide documentation for having had a vasectomy (with documented infertility)
- f. Have best corrected visual acuity (BCVA) of +1.0 log of the minimum angle of resolution (logMAR -Snellen equivalent of 20/200) or better in the fellow eye (non-study eye)
- g. Able to self-instill the IP (or have a caregiver available to instill all doses of the IP, as instructed)
- h. Have an intraocular pressure (IOP) of > 8 mmHg and  $\le 22$  mmHg in the surgery eye (study eye)

## 3.2 Exclusion Criteria

The following are exclusion criteria for prospective study subjects to be confirmed at Visit 1 (Day -14 – Day -2) prior to randomization. The sponsor will not grant any protocol eligibility waivers.

- a. Have a history of Fuchs' dystrophy in the study eye
- b. Have a history of diabetic retinopathy (with visual impairment) and/or previous vitrectomy in the study eye within the last 2 years
- c. Have any sign of iritis or scleritis in the study eye

- d. Have a history of glaucoma surgery in the study eye within the last 2 years
- e. Have an existing diagnosis of severe dry eye in the study eye
- f. Have known hypersensitivity or poor tolerance to any component of the IP or any of the procedural medications such as anesthetic and/or fluorescein drops, dilating drops, etc.
- g. Have an acute ocular infection (bacterial, viral or fungal) or active ocular inflammation in the study eye
- h. Have any extraocular/intraocular inflammation in the study eye noted prior to surgery (blepharitis is allowed if scurf only without any concurrent conjunctivitis or lid erythema/edema) or ongoing, unresolved uveitis
- i. Use of the following disallowed medications within a specified amount of time before surgery:
  - topical, inhaled, or oral corticosteroids within 15 days
  - depot-corticosteroids within 45 days (triamcinolone within 90 days)
  - topical, systemic, or inhaled nonsteroidal anti-inflammatory drugs (NSAIDs) within 1 week (with the exception of low-dose aspirin)
  - ocular or systemic antihistamines, or mast cell stabilizers within 1 week
  - other analgesics and use of acetaminophen (Tylenol®) within 48 hours
  - any medication that the investigator feels may interfere with the study parameters
- j. Have any active or chronic/recurrent ocular or systemic disease that is uncontrolled and likely to affect wound healing (e.g., diabetes mellitus, systemic connective tissue disease, severe atopic disease)
- k. Have known blood dyscrasia or bone marrow suppression
- 1. Have any active corneal pathology noted in the study eye
- m. Have any intraocular inflammation (cells or flare in anterior chamber) or ocular pain (greater than 0) on the pain scale in either eye
- n. Have had radial keratotomy, corneal transplant, or LASIK in the study eye within the last 2 years
- o. Be currently pregnant, nursing, or planning a pregnancy, or be a woman that has a positive pregnancy test
- p. Are currently suffering from alcohol and/or drug abuse
- q. Prior participation in this study protocol
- r. Prior participation in InSite Vision Protocol C-16-305-003

- s. Have prior (within 30 days of beginning study treatment) or anticipated concurrent use of an investigational drug or device
- t. Have a condition or a situation which, in the investigator's opinion, may put the subject at increased risk, confound study data, or interfere significantly with the subject's study participation
- u. Contact lens wear during the dosing period on Days -1 to Day 14
- v. Use of any medication the investigator feels may interfere with the study parameters

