**Table 1: Schedule of Assessments** 

	Screening/ Randomization Phase	Dosing Phase (16 Days)				Evaluation Phase (15 Days)		
Evaluation 	Visit 1 Day -14 to Day -2	Phone Call Day -3 (±1)	Visit 2 Day 0 (Day of Surgery)	Visit 3 Day 1 (+1)	Visit 4 Day 8 (±1)	Visit 5 Day 15 (+1)	Visit 6 Day 18 (-1/+2)	Visit 7 Day 29 (± 2)
Written Informed Consent	X							
Demographics	X							
Entry Criteria	X							
Medical/Medication History	X							
Urine Pregnancy Test	X							X
Slit Lamp Biomicroscopy 	X			X	X	X	X	X
Visual Analog Scale	X			X	X	X	X	X
Intraocular Pressure	X			X	X	X	X	X
Best Corrected Visual Acuity	X			$X^3$	X	X	X	X
Ophthalmoscopy 	X					X	X 	X 
Confirm and Document Subject Eligibility	X							
Randomization	X							
Dispense IP and Pain/Dosing Diary	X							
Instruct Subject on IP and Dosing/Pain Diary	X							
AE Assessment	X	X	X	X	X	X	X	X
Dosing Reminder Call		X						
Update Concomitant Medications			X	X	X	X	X	X
Review Pain/Dosing Diary			X	X	X	X	$X^4$	X 
Collect IP						X	X 	X 
Collect Pain/Dosing Diary							X	X 
Exit Subject From Study			_					X

IP = Investigational Product; AE = adverse event; eCRF = electronic case report form

<sup>1All eye exams are to be conducted in the study eye only. The fellow eye (non-study eye) may be examined at the investigators' discretion.

<sup>2Performed by a board-certified ophthalmologist.

<sup>3A pinhole test may be employed at Day 1 (Visit 3).

<sup>4Dosing terminates on Day 14. Pain is assessed through the evening of Day 17.

<sup>5If not completed at previous visit.

Note: Unscheduled visits may occur during the study period. All assessments will be recorded on the eCRF for unscheduled visits, but it is up to the investigator which assessments to conduct. If the subject exits early, all Visit 7 assessments should be conducted, including ophthalmoscopy if not obtained at Day 15 (Visit 5).

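### Can exclusions i and u be confirmed at Visit 1 when the periods they cover run to surgery or to Day 14?

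*Protocol*

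**What the plan says.** The lead-in to Protocol section 3.2 describes what follows as "exclusion criteria for prospective study subjects to be confirmed at Visit 1", gives the range Day -14 to Day -2, places the check before randomisation, and adds: "The sponsor will not grant any protocol eligibility waivers". Table 1 agrees. The row "Confirm and Document Subject Eligibility" is marked at Visit 1 only, as are the entry-criteria and randomisation rows.

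Two exclusions cover time after that visit:

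- Exclusion i is headed "Use of the following disallowed medications within a specified amount of time before surgery". Its timed items are 15 days for topical, inhaled or oral corticosteroids, "depot-corticosteroids within 45 days (triamcinolone within 90 days)", 1 week for NSAIDs and for antihistamines or mast cell stabilisers, and 48 hours for other analgesics and acetaminophen. Its last item, left to the investigator's judgement, has no window.
- Exclusion u reads "Contact lens wear during the dosing period on Days -1 to Day 14".

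Three other criteria bear on the point. Inclusion a requires that cataract surgery is already scheduled. Inclusion d reads "Are willing to avoid disallowed medication for the duration of the study". Exclusion s looks forward explicitly, with the phrase "anticipated concurrent use of an investigational drug or device".

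**The concern.** A criterion that must be confirmed before randomisation should depend only on what is known or expected then. Exclusions i and u are worded as actual use and actual wear, partly or wholly after Visit 1. A subject could take acetaminophen on Day -1, or wear a lens on Day 10, and so literally meet an exclusion that cannot be waived after being randomised and dosed.

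The first medication update after Visit 1 is at Visit 2 on Day 0; the Day -3 call carries only the dosing reminder and the adverse event question. By Visit 2 the two Day -1 doses are due to have been taken. One site might record an ineligible enrolment where another records a protocol deviation. If subjects were then dropped from follow-up or analysis for what they did after randomisation, the randomised comparison of anterior chamber cell grade 0 at Day 15 would lose some of its protection.

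**Working it through.** **Inputs.** Visit 1 falls on day d, from -14 to -2, which is 13 permitted days (section 3.2, Table 1). Surgery is Day 0. The windows W before surgery are 2, 7, 15, 45 and 90 days (exclusion i). The lens period is Day -1 to Day 14 (exclusion u), or 14 - (-1) + 1 = 16 days. The protocol gives no figure of its own to reproduce here.

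**Formula.** In whole days, the part of a window already past at Visit 1 is max(0, W + d), and the part still ahead is min(W, |d|).

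| Item | Past at Day -14 | Past at Day -2 | Ahead at Day -14 / Day -2 |
|---|---|---|---|
| Analgesics, 48 hours | 0 of 2 | 0 of 2 | 2 / 2 |
| NSAIDs, antihistamines, mast cell stabilisers, 1 week | 0 of 7 | 5 of 7 | 7 / 2 |
| Corticosteroids, 15 days | 1 of 15 | 13 of 15 | 14 / 2 |
| Depot corticosteroids, 45 days | 31 of 45 | 43 of 45 | 14 / 2 |
| Triamcinolone, 90 days | 76 of 90 | 88 of 90 | 14 / 2 |
| Contact lenses, 16 days | 0 of 16 | 0 of 16 | 16 / 16 |

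The 1-week items have nothing past on Days -14 to -7, which is 8 of the 13 days. The 15-day item has more than half still ahead when |d| > 7.5, that is on Days -14 to -8, or 7 of 13 days. No item is complete on any of the 13 days.

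**What the count shows.** Any window that ends at a future surgery is incomplete at a visit held before surgery. The zero out of 13 therefore follows from the choice of surgery as the anchor. It does not measure misclassification or harm.

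**What the protocol does with the part still ahead.**

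1. *When eligibility is judged.* The lead-in speaks of prospective subjects, and Table 1 marks the check once. No text keeps the criteria running after randomisation. The no-waiver sentence governs admission to the trial; it does not say that a later event cancels it.
2. *Exclusion i.* Because inclusion a requires a scheduled operation, the site has a date to count back from and can ask about recent, ongoing and planned use. The interval in question, Visit 1 to surgery, lies within the study duration to which inclusion d applies. Inclusion d and exclusion i use the same term for the medicines, and exclusion i supplies the list.
3. *Exclusion u.* The whole lens period follows Visit 1, so a confirmation at that visit can only concern intended wear. Inclusion c (willingness and ability to comply with instructions) covers lens avoidance if the subject is instructed to avoid lenses. Exclusion t lets the investigator decline someone whose circumstances could confound the data.
4. *Later use.* Medication use between Visit 1 and surgery can be recorded at the existing Visit 2 update. Whether such use counts as a deviation, and how the subject enters the analysis sets, is commonly set out in the statistical analysis plan.

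**The case for a change.** The strongest case for a change is textual. Exclusion s shows that the authors had a prospective form of words available and did not use it for i or u. Willingness under inclusion d is a different condition from use, and no criterion names willingness to forgo lenses. A statistical analysis plan can define analysis sets, but it cannot tell a site whether a subject has become ineligible. Section 2.0 adds some weight: anyone who stops the investigational product for any reason is withdrawn, so a site that stopped treatment over a supposed eligibility breach could put the Day 15 assessment at risk. The remedy would be a matter of wording.

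Part of this stands. The drafting is uneven. Exclusion u is the clearest instance and the 48-hour item of exclusion i the next. The rest does not carry the point to a change. The route to a lost Day 15 value needs a site to treat later behaviour as cancelling eligibility and then to stop treatment, and the protocol directs neither step. Differing classification between sites is possible but is not shown. A rewrite is also less simple than it looks: a statement that later use is only a deviation would have to be squared with section 2.0, where rescue medication for lack of efficacy must follow withdrawal.

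**Conclusion.** The observation is accurate as to wording: on 0 of 13 permitted Visit 1 days is any of these periods complete, and exclusion u and the 48-hour item lie wholly ahead. No change to the plan follows. This is a drafting inconsistency that sites can resolve sensibly by reading i and u as known or anticipated use or wear, which is the only way they can be confirmed when section 3.2 requires. For exclusion i, inclusion d already supplies most of the forward-looking commitment. Rewording would add no check and alter no sample size, error rate or endpoint definition.

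This rests on two assumptions: that sites treat eligibility as settled at Visit 1, as Table 1 indicates, and that the statistical analysis plan deals with later breaches in the usual way. How often such breaches occur, and what they would do to the Day 15 result, cannot be computed from the protocol. The day counts are in whole days: a late visit on Day -2 followed by an early operation could place a few hours of the 48-hour window in the past, but never all of it.

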### 4.0 STUDY TREATMENT AND DRUG/DOSAGE ADMINISTRATION

Subjects will be randomized in a 2:1 ratio to 1 of 2 treatment groups:

- 1. ISV-305 (0.1% dexamethasone in DuraSite 2) BID (160 subjects)
- 2. DuraSite 2 Vehicle BID (80 subjects)

One drop of IP will be self-instilled by the subject (or instilled by caregiver) BID, in the surgery eye (study eye) for 16 days: the day prior to surgery, the day of surgery and postoperatively for 14 days.

The study coordinator or investigator will instruct the subjects on the proper administration of their IP.

Subjects (and caregiver as appropriate) will be instructed to bring their pain and dosing diary to each visit for review with site staff and for collection of diary on Day 18 (Visit 6), and to return all bottles of IP on Day 15 (Visit 5) for collection.

## 5.0 CONTRAINDICATIONS, WARNINGS AND PRECAUTIONS

Contraindications, warning and precautions for ophthalmic dexamethasone as described in the labeling of the approved product Maxidex (0.1% dexamethasone) are presented below.

Use of ophthalmic dexamethasone is contraindicated in epithelial herpes simplex (dendritic keratitis), vaccinia, varicella, and most other viral diseases of the cornea and conjunctiva, tuberculosis of the eye and fungal disease of ocular structures.

Class warnings for corticosteroids such as dexamethasone are well known and state that prolonged use may result in ocular hypertension and/or glaucoma, with damage to the optic nerve, defects in VA and fields of vision, and posterior subcapsular cataract formation. Prolonged use may also suppress the host response and thus increase the hazard of secondary ocular infections. In diseases causing thinning of the cornea or sclera, perforations have been known to occur with the use of topical corticosteroids. In acute purulent conditions of the eye, corticosteroids may mask infection or enhance existing infection. It is recommended that if corticosteroids are used for 10 days or longer, intraocular pressure should be routinely monitored.

The possibility of persistent fungal infections of the cornea should be considered after prolonged corticosteroid dosing.

Subjects are excluded from participating in the study if there is known hypersensitivity or poor tolerance to any component of the IP or any of the procedural medications such as anesthetic and/or fluorescein drops, dilating drops, etc. See Exclusion Criterion f.

## 6.0 CLINICAL ASSESSMENTS/PROCEDURES

#### 6.1 Schedule of Assessments

The procedures and measurements to be evaluated at each study visit are shown in Table 1: Schedule of Assessments.

**Table 1: Schedule of Assessments** 

	Screening/ Randomization Phase	Dosing Phase (16 Days)				Evaluation Phase (15 Days)		
Evaluation 	Visit 1 Day -14 to Day -2	Phone Call Day -3 (±1)	Visit 2 Day 0 (Day of Surgery)	Visit 3 Day 1 (+1)	Visit 4 Day 8 (±1)	Visit 5 Day 15 (+1)	Visit 6 Day 18 (-1/+2)	Visit 7 Day 29 (± 2)
Written Informed Consent	X							
Demographics	X							
Entry Criteria	X							
Medical/Medication History	X							
Urine Pregnancy Test	X							X
Slit Lamp Biomicroscopy 	X			X	X	X	X	X
Visual Analog Scale	X			X	X	X	X	X
Intraocular Pressure	X			X	X	X	X	X
Best Corrected Visual Acuity	X			$X^3$	X	X	X	X
Ophthalmoscopy 	X					X	X 	X 
Confirm and Document Subject Eligibility	X							
Randomization	X							
Dispense IP and Pain/Dosing Diary	X							
Instruct Subject on IP and Dosing/Pain Diary	X							
AE Assessment	X	X	X	X	X	X	X	X
Dosing Reminder Call		X						
Update Concomitant Medications			X	X	X	X	X	X
Review Pain/Dosing Diary			X	X	X	X	$X^4$	X 
Collect IP						X	X 	X 
Collect Pain/Dosing Diary							X	X 
Exit Subject From Study			_					X

IP = Investigational Product; AE = adverse event; eCRF = electronic case report form

<sup>1All eye exams are to be conducted in the study eye only. The fellow eye (non-study eye) may be examined at the investigators' discretion.

<sup>2Performed by a board-certified ophthalmologist.

<sup>3A pinhole test may be employed at Day 1 (Visit 3).

<sup>4Dosing terminates on Day 14. Pain is assessed through the evening of Day 17.

<sup>5If not completed at previous visit.

Note: Unscheduled visits may occur during the study period. All assessments will be recorded on the eCRF for unscheduled visits, but it is up to the investigator which assessments to conduct. If the subject exits early, all Visit 7 assessments should be conducted, including ophthalmoscopy if not obtained at Day 15 (Visit 5).

#### **6.2** Examination Procedures

The following ophthalmic examinations will be conducted in the surgery eye (study eye) at intervals specified in Table 1, The Schedule of Assessments. The fellow eye (non-study eye) may be examined at the investigators' discretion.

- **Best Corrected Visual Acuity (BCVA):** BCVA will be measured at every visit except Visit 2 (Surgery; Day 0). The Early Treatment Diabetic Retinopathy (ETDRS) log of the minimum angle of resolution (logMAR) will be used to measure BCVA.
- Intraocular Pressure (IOP): IOP will be measured at every visit except Visit 2 (Surgery; Day 0) in mmHg using an applanation tonometer.
- **Ophthalmoscopy**: Ophthalmoscopy will be performed at Visit 1 (Day -14 to Day -2) and Visit 5 (Day 15) by a board-certified ophthalmologist.
- **Biomicroscopy:** Slit lamp biomicroscopy, including the evaluation of ACC and anterior chamber flare (ACF), chemosis, bulbar conjunctival injection, ciliary injection, corneal edema, and keratic precipitates will be conducted by a board-certified ophthalmologist at every visit except Visit 2 (Surgery; Day 0).
- Visual Analog Scale (VAS): Eye pain/discomfort and photophobia will be evaluated at every visit except Visit 2 (Surgery; Day 0) using a Visual Analog Scale (VAS), scoring from 0 to 100 using a mark on a 100 mm line (0 = absent; 100 = maximum).
- Pain assessment via diary (Pain Diary): Surgery eye pain will be evaluated prior to each IP dose using a pain scale included in the pain and dosing diary that subjects complete at home.

## 7.0 EVALUATION, RECORDING AND REPORTING OF ADVERSE EVENTS

All AEs either observed by the investigator or study site staff or reported by the subject spontaneously or in response to a direct question regarding the subject's health by the investigator will be recorded in the source document and AE eCRF.

Events reported before signing the consent form should be recorded as medical history; once the ICF is signed new conditions or worsening of existing conditions or episodes that increase in frequency should be recorded as AEs in the source document and AE eCRF.

To standardize the collection of AEs during a study, subjects should be asked a standard question to elicit AEs: "Have you had any problems since your last visit or telephone call?" and "What is the status of [list previously reported unresolved AEs]?" Subjects will also be instructed to contact the investigator immediately if they note any unusual systemic or ocular AEs between visits.

Throughout the course of the study, the investigator must remain alert to possible adverse experiences or untoward findings. If adverse experiences occur, the first concern will be the safety of the subject. Appropriate medical intervention will be provided by the investigator.

The collection, review and management of safety data (AEs and SAEs) will be conducted in compliance with the requirements of the FDA as well as the local IRB/Independent Ethics Committee (IEC).

#### 7.1 Definitions

#### **Adverse Event**

An AE is any untoward medical occurrence associated with the use of an IP in humans, whether or not considered related to the IP.

An AE can therefore be any unfavorable and unintended sign (including an abnormal laboratory finding, for example), symptom, or disease temporally associated with the use of an IP, without any judgment about causality. An AE can arise from any use of the IP (e.g., off-label use, use in combination with another drug) and from any route of administration, formulation or dose, including overdose.

Medical conditions or diseases present before a subject starts study treatment are only considered AEs if they worsen after the subject signs informed consent.

Diagnostic and therapeutic non-invasive and invasive procedures, such as surgery, should not be reported as AEs. However, the medical condition for which the procedure was performed should be reported if it meets the definition of an AE. For example, an acute appendicitis that begins during the AE-reporting period should be reported as the AE and the resulting appendectomy noted according to the eCRF completion guideline.

## **Adverse Event Reporting Period**

The AE reporting period for this study begins upon signing the consent form and ends at the completion of the subjects' final visit exam. All AEs that occur in study subjects during the AE-reporting period must be reported in the source documents and on the AE eCRF, whether or not the event is considered related to the IP. In addition, any known untoward event that occurs subsequent to the AE reporting period that the investigator assesses as possibly related to the IP should be recorded in the source documents and reported to the sponsor or designee.

## **Serious Adverse Event (SAE)**

An SAE is an event that, in the view of either the investigator or sponsor, results in any of the following outcomes:

- death
- a life-threatening AE or sight-threatening AE, where ophthalmics are involved
- inpatient hospitalization or prolongation of existing hospitalization
- a persistent or significant incapacity or substantial disruption of the ability to conduct normal life functions
- a congenital anomaly/birth defect

• an important medical event that may not result in death, be life-threatening/sight-threatening, or require hospitalization may be considered serious when, based upon appropriate medical judgment, they may jeopardize the subject and may require medical or surgical intervention to prevent one of the outcomes listed above. Examples of such events are intensive treatment in emergency room or at home for allergic bronchospasm; blood dyscrasias or convulsions that do not result in hospitalization; or development of drug dependency or drug abuse.

The criterion of inpatient hospitalization is met if the subject is admitted to the hospital as the result of an AE, even if the subject is released on the same day. An emergency room visit does not qualify as "inpatient hospitalization" unless the subject is admitted to the hospital during the visit; however, the reason for the emergency room visit may qualify as an SAE based on another SAE criteria (e.g., life threatening or medically significant event).

